After induction, patients demonstrating complete remission or partial remission will continue to consolidation. Patients in CRi (ANC <  $1.0 \times 10^9$ /L or platelets <  $100 \times 10^9$ /L) will stop Venetoclax for up to four weeks to allow for cytopenia recovery. If the ANC recovers to  $\ge 1.0 \times 10^9$ /L and the platelets recover to  $\ge 100 \times 10^9$ /L, consolidation will ensue. If there is not full ANC AND platelet recovery to the aforementioned levels, consolidation will be omitted, and patients will enter the maintenance phase with Venetoclax alone provided they do not have any grade 3-4 cytopenias. The previously assigned Venetoclax dose will be resumed and the maintenance rules for Venetoclax dose adjustments or discontinuation will apply (see section 6.2.2). If however patients have a grade 3-4 cytopenia despite holding Venetoclax for four weeks, they will be *removed from study* [NOTE: this applies to both induction and consolidation.]

Cycle 2: The second cycle (consolidation) will consist of GO 3 mg/m^2 IV infusion (up to one 4.5 mg vial) on days +1, and +4, in addition to daily oral administration of Venetoclax at the assigned dose. A bone marrow assessment will occur on day 28 regardless of cytopenias and those with CR, CRi, or at least a partial remission will continue onto maintenance therapy with Venetoclax alone. The previously assigned Venetoclax dose will be resumed and the maintenance rules for Venetoclax dose adjustments or discontinuation will apply (see section **6.2.2**).

After day 28, in the absence of leukemia in the BM, where there is a grade 3-4 cytopenia (thrombocytopenia or neutropenia), Venetoclax should be held for up to four weeks to allow recovery of counts to platelets  $\geq 50 \times 10^9$ /L and ANC  $\geq 1.0 \times 10^9$ /L (to allow entry into Maintenance Phase). Those who continue to have a grade 3-4 cytopenia will be taken off study.

Patients with treatment failure (see Section 9.1) will be taken off study. Please note that any patient with residual disease (with at least PR) may move onto consolidation regardless of blood counts.

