# **5.5** Maintenance Phase: (see also section 6.2.2, Tables 7, 8)

Please note that any patient with residual disease (with at least PR) may move onto maintenance regardless of blood counts.

Patients who enter a maintenance phase require platelets  $\geq 50 \ge 10^{9}/L$  and an ANC  $\geq 1.0 \ge 10^{9}/L$ . If a subject presents with a Grade 4 cytopenia for more than 1 week during Maintenance phase, unless it is thought to be due to the underlying disease, venetoclax dosing should be interrupted until platelets  $\geq 50 \ge 10^{9}/L$  and ANC  $\geq 1.0 \ge 10^{9}/L$ .

During Maintenance, for subjects, in CR/CRi, receiving venetoclax who required >1 interruption or delay of study drug administration for grade 4 cytopenias, venetoclax, at dose prescribed for that cohort, should be administered for 21 days out of 28 days during each of the subsequent cycles. If, despite these modifications, a subject continues to have persistent grade 4 cytopenias, venetoclax should be administered for 14 days out of 28 days during each of the subsequent cycles.

If grade 3 cytopenias (i.e., ANC <  $1.0 \times 10^9$ /L and/or platelets <  $50 \times 10^9$ /L) persist please discuss with PI, however those who still continue to have a grade 4 cytopenia should be taken off study.

Venetoclax therapy will be continued daily at the previously assigned dose for as long as patients continue to benefit or until disease progression or unacceptable toxicity.

Patients who enter the maintenance phase in partial remission should have a bone marrow assessment after the first month of maintenance therapy (cycle 3). Those with an improved response should continue with maintenance Venetoclax. Those with stable disease should continue treatment if the drug is well-tolerated and if the primary hematologist believes that Venetoclax is of benefit. If there is disease progression, patients should be taken off study.

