#### 7.2 Long Term Follow-up Evaluations

All subjects will be followed until documented disease progression. Subjects who discontinue treatment for any reason without documented disease progression will be followed for disease progression every 2 months ( $\pm 14$  days) for 6 months.

Once disease progression is documented, subjects will enter a survival follow up period every 2 months ( $\pm 14$  days) for 6 months from the time of documented progression.

Follow up may be accomplished via clinic visit, phone call, or other avenues as appropriate.

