# 9. CRITERIA FOR DISEASE EVALUATION

#### 9.1 Definitions of Response to Treatment in AML

Disease will be assessed according to the International Working Group Criteria.

Category	Definition					
Treatment Success categories						
Complete remission (CR)	Bone marrow blasts < 5%; absence of blasts with Auer rods; absence of extramedullary disease; absolute neutrophil count > $1.0 \times 10^{9}/L$ ( $1000/\mu$ L); platelet count > $100 \times 10^{9}/L$ ( $100,000/\mu$ L); independent of red cell transfusions					
CR with incomplete recovery (CRi)	All CR criteria except for residual neutropenia $< 1.0 \times 10^{9}/L$ (1000/µL) or thrombocytopenia $< 100 \times 10^{9}/L$ (100,000/µL)					
Partial remission (PR)	All hematologic criteria of CR; decrease of bone marrow blast percentage to 5% to 25%; and decrease of pretreatment bone marrow blast percentage by at least 50%					
Treatment Failure categories						
Resistant Disease	Failure to achieve CR or CRi or failure to achieve CR, CRi, or PR; only includes patients surviving $\geq$ 7 days following completion of initial treatment, with evidence of persistent leukemia by blood and/or bone marrow examination					
Death in aplasia	Deaths occurring $\geq$ 7 days following completion of initial treatment while cytopenic; with an aplastic or hypoplastic bone marrow obtained within 7 days of death, without evidence of persistent leukemia					
Death from indeterminate cause	Deaths occurring before completion of therapy, or $< 7$ days following its completion; or deaths occurring $\ge 7$ days following completion of initial therapy with no blasts in the blood, but no bone marrow examination available					

Adapted from International Working Group Criteria

In patients with abnormal cytogenetics at diagnosis, CR (or CRi) will be delineated as above plus evidence of complete cytogenetic response (also known as CRc)—defined as a reversion to normal cytogenetics.

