#### 9.2 Definitions of Survival Endpoints for AML

Overall Survival	All evaluable patients entered into trial; measured from the date of entry to the date of death from any cause; patients not known to have died at last follow- up are censored on the date they were last known to be alive				
Relapse-free Survival	Only patients achieving CR or CRi; measured from the date of achievement of a remission until the date of relapse or death from any cause; patients not known to have relapsed or died at last follow-up are censored on the date they were last examined				
Event-free Survival	All patients entered into trial; measured from the date of entry to the date of treatment failure, disease relapse, or death from any cause; patients not known to have any of these events are censored on the date they were last examined				
Adapted from European LeukemiaNet. 					

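### EFS has no event for progression after partial remission, and section 9.1 leaves open whether partial remission is itself a failure, so the EFS estimate depends on an unresolved choice

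*Combined protocol and SAP*

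**What the plan says.** Section 9.2 starts the EFS clock at trial entry for all patients, with time "measured from the date of entry to the date of treatment failure, disease relapse, or death from any cause". Otherwise "patients not known to have any of these events are censored on the date they were last examined".

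Section 9.1 places CR, CRi and PR under "Treatment Success categories". The failure categories are Resistant Disease and two kinds of death. Resistant Disease carries two alternatives in one row: "Failure to achieve CR or CRi or failure to achieve CR, CRi, or PR".

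The treatment sections then act on these categories:

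- Section 5.4: "Patients with treatment failure (see Section 9.1) will be taken off study". The same paragraph adds that "any patient with residual disease (with at least PR) may move onto consolidation regardless of blood counts", and after cycle 2 patients in at least PR go on to maintenance.
- Section 5.5: patients who enter maintenance in PR have a marrow after cycle 3. Stable disease may continue. "If there is disease progression, patients should be taken off study".
- Section 6.3: documented progression is a reason to stop protocol therapy, and the marrow-based reason is a response below PR.
- Section 7.2: "All subjects will be followed until documented disease progression". Survival contacts follow every 2 months for 6 months, and may be by phone.

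Section 9 defines neither progression nor relapse, and gives no date to assign to a treatment failure.

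**The concern.** Progression governs treatment and follow-up in this protocol but is absent from EFS. A patient in PR has not failed under sections 5.4 and 6.3. Relapse is not an obvious label either, because section 9.2 otherwise uses it only for RFS, which is restricted to CR/CRi. If leukemia then progresses on maintenance, the patient goes off study for progressive disease and yet carries no EFS event.

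Two analysts applying the text faithfully could code that patient differently. One records a failure when initial treatment ends in PR. The other records nothing until death, or censors at the last examination. EFS is a named secondary endpoint in a small trial, so a few such patients would visibly change the curve.

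**Working it through.** The plan states no EFS rate, median, event count or power, so there is no figure to reproduce. The check has two parts.

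**1. The text under three readings, for a patient in PR after cycle 2 who later progresses**

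- Reading A: first alternative of Resistant Disease (CR or CRi not reached). The event falls at the end of initial treatment, before progression. This conflicts with the success heading in 9.1, and with 5.4, which takes failures off study yet lets PR patients continue.
- Reading B: second alternative (CR, CRi or PR not reached), with 9.2 as written. PR is not a failure, and progression is not an event. The next event is death. This agrees with 5.4, 5.5 and 6.3.
- Reading C: as B, with progression counted.

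**2. Illustrative size at 6 months**

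Every rate here is an assumption, none is from the documents: CR/CRi 30% with median remission 8 months; PR 5–20%; median 2–4 months from day 56 to progression; median 2–4 months from progression to death; all other patients fail at day 28; exponential times; no censoring.

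Time from day 56 to 6 months: t = 6 − 56/30.44 = 4.16 months. Rates: λ1 = ln 2 / (median to progression), λ2 = ln 2 / (median from progression to death).

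B exceeds C by the PR rate multiplied by the chance of having progressed and being alive at 6 months:

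P = λ1/(λ1 − λ2) × (exp(−λ2 t) − exp(−λ1 t)), or λt·exp(−λt) when the rates are equal.

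- Medians 2 and 2: 1.442 × 0.2365 = 0.34
- Medians 2 and 4: 0.50
- Medians 4 and 2: 0.25
- Medians 4 and 4: 0.721 × 0.4863 = 0.35

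The gap is therefore 0.25 to 0.50 times the PR rate: 5% × 0.25 = 1.25 points at the low end, and 20% × 0.50 = 10 points at the high end. A simulation of 400,000 patients per scenario agrees:

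| PR rate | A: PR is failure | B: progression not an event | C: progression counted | B − C (points) |
|---|---|---|---|---|
| 5% | about 21% | 23.9–25.1% | 22.1–23.4% | 1.2–2.5 |
| 10% | about 21% | 26.6–29.3% | 23.2–25.8% | 2.4–4.9 |
| 20% | about 21% | 32.5–37.7% | 25.6–30.7% | 5.0–10.0 |

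Reading A lies below C by the PR rate times exp(−λ1 t), which is 0.24 to 0.49: from 5% × 0.24 = 1.2 points to 20% × 0.49 = 9.8 points. The two alternatives therefore err in opposite directions relative to C.

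**Scale in this trial.** The synopsis gives N = 15–24. One patient is 1/24 = 4.2 to 1/15 = 6.7 points of a crude proportion. PR rates of 5–20% mean 15 × 0.05 = 0.8 to 24 × 0.20 = 4.8 patients.

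**Median.** In this illustration the share failing at day 28 is 100 − 30 − PR: 65%, 60% and 50% for PR of 5%, 10% and 20%. Above one half, the median EFS falls among those early failures whatever is done with PR.

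**The case against.** The strongest reply is that the gap may not exist. Treatment failure is an EFS event, and the first alternative of Resistant Disease makes a best response of PR a failure. The event then precedes progression, and EFS is not overstated. This stands as an ambiguity: the success heading and sections 5.4 and 6.3 favour the other alternative but do not delete this one.

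A second reply is that relapse is not defined as loss of CR/CRi. Section 9.2 restricts only the RFS population, and section 8.1.3 speaks of relapse after initial response and groups it with non-response as treatment failure. An analyst might code loss of PR under either term. That is possible, but the same section goes on to mention CR samples, so it does not settle the matter.

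A third reply concerns size. PR in section 9.1 requires all the hematologic criteria of CR, so it may be uncommon. Some PR patients may improve (5.5) or leave for transplant (5.6). Post-progression contacts by phone may mean censoring near progression rather than months counted as event-free; such censoring can still bias upward, but by a different amount. All of this stands. So does the point that EFS is descriptive, with no threshold or decision attached.

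A reader might infer that EFS is certainly inflated, by a known amount, and its median with it. The documents do not support that. The direction depends on which alternative is used, and the size depends on assumed rates. For example, PR of 10–25% with medians of 1.5–2 and 3–6 months gives P = 0.44–0.63 and a gap of about 4–16 points, from inputs just as arbitrary. The median need not move when most patients fail early.

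**Conclusion.** The point holds in a qualified form. On the reading under which the protocol operates, with PR a success, a partial responder who progresses and is taken off study has no EFS event at progression, and EFS is overstated relative to a definition that counts it. On the first alternative of Resistant Disease, the same patient has already failed, in conflict with how sections 5.4 and 6.3 treat PR. The estimate rests on a choice that the plan does not make.

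The documents do not fix the size. Under the stated assumptions it is about 1–10 points at 6 months, with each patient worth about 4–7 points. Dose escalation, the MTD and the stopping rules rest on DLTs and are unaffected. The change is worth making before EFS is analysed, because the affected patients are foreseeable and the repair is short.

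**What to change.** In sections 9.1 and 9.2:

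1. State that, for EFS, treatment failure means failure to achieve CR, CRi or PR, in line with sections 5.4 and 6.3.
2. Add disease progression, including progression from PR, to the EFS events alongside treatment failure, relapse and death.
3. Define progression for this purpose, since section 9 does not.
4. Date treatment failure and progression at the first marrow or blood assessment that documents them.

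The cost is a few lines of text, including a short definition of progression. Progression is already documented for sections 6.3 and 7.2, so no new visits are needed. EFS becomes slightly less favourable than under the present operational reading.

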# 5.2 Definition of Dose-limiting Toxicities

Dose-limiting toxicities (DLTs) are defined as an adverse event related (possible, probable or definite) to Venetoclax and/or Gemtuzumab Ozogamicin fulfilling one of the following criteria:

 Hematologic toxicity: treatment-related grade 3 or worse neutropenia and/or thrombocytopenia due to bone marrow hypocellularity present at the end of cycle one (day 28) with an additional 28 days allowed for count recovery (i.e. present at day 56); specifically grade 3 or worse neutropenia or thrombocytopenia with the bone marrow documented to be free of leukemic infiltration. Note: patients who enter the study with grade 3 or worse cytopenias will not be evaluable for hematologic dose-limiting toxicities.

• Non-hematologic toxicity: any grade 3 or worse treatment-related toxicity occurring within the first cycle (excluding grade 3-4 infections during cycle one).

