#### Consider discontinuing Venetoclax if toxicities recur despite two dose duration reductions

# 6.3 **Protocol Therapy Discontinuation**

In addition to discontinuation due to therapy-related toxicities as outlined in section **6.1**, a subject will also be discontinued from protocol therapy and then followed up per protocol under the circumstances outlined below. The reason for discontinuation of protocol therapy will be documented on the electronic case report form (eCRF) and should also be discussed with the study sponsor-investigator.

- Documented disease progression
- Unacceptable toxicity
- The treating physician believes a change of therapy would be in the best interest of the subject
- Follow-up bone marrow biopsy demonstrates either significant residual leukemic blasts or significant cytoreduction with a high percentage residual leukemic blasts, but BM study is deemed by the hematopathologist to demonstrate less than a partial response.
- Bone marrow biopsy during maintenance phase shows stable disease but the treating hematologist believes that the Venetoclax is no longer of benefit.
- DLT as defined above or if there is grade 3 neutropenia or thrombocytopenia after holding Venetoclax for four weeks at the end of cycles 1 or 2
- Patient is unable to comply with protocol requirements
- The subject requests to discontinue protocol therapy, whether due to unacceptable toxicity or for other reasons. If a subject decides to prematurely discontinue protocol therapy ("refuses treatment"), the subject should be asked if he or she may still be contacted for further scheduled study assessments. The outcome of that discussion should be documented in both the medical records and in the eCRF.
- A female subject becomes pregnant
- Development of a second malignancy (except for basal cell carcinoma or squamous cell carcinoma of the skin) that requires treatment which would interfere with this study.
- If protocol therapy is interrupted for  $\geq 30$  days.
- Lost to follow up. If a research subject cannot be located to document survival, the subject may be considered "lost to follow-up." All attempts to contact the subject must be documented.

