# 12.3 Sample Size and Accrual

A standard "3 + 3" design will be used to establish the maximum tolerated dose. The maximum tolerated dose is defined as the dose level at which fewer than 33% of subjects experience a dose limiting toxicity. An expansion cohort of 6 patients will be carried out at the maximum tolerated dose, which will be the recommended Phase II dose.

This study is a traditional '3 + 3' design without de-escalation, a specified A + B dose finding study with parameters of A = B = 3,  $c_L = 0$ ,  $c_U = 2$ , and  $C_U = 1$ . The associated target quantiles for our study are  $\Gamma_A = 0.35$  and  $\Gamma_A = 0.26$ . Hence, the dose selected by this design has a toxicity rate below 0.26 and above  $C_U/(A + B)$  on average. In simulation studies, the apparent selected dose with our targeted N=18-24 (n=9-18, plus 6) selects a dose with toxicity rate near 0.2. In this scenario, the '3 + 3' design  $\Gamma_U = (C_U + 1)/(A + B) = 2/(3 + 3) = 0.33$  is our upper bound. To evaluate the quality of estimation of the target dose per average sample size increase, we reviewed simulation studies of this design under conditions of A = B = 3 with values of change ( $\Delta$ ) of either 0.35 or 0.70. Within the average sample size range of 16.2 to 21.8, between 78% and 89% correct dose recommendations were achieved, where tendencies of higher  $\Delta$  resulted in greater percent correct dose recommendations [see ref. 45 for further review].

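### EFS has no event for a patient who stops in cycle 1 alive, without a response and without later evidence of leukemia, so reported EFS is biased upward by an amount the documents do not fix

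*Combined protocol and SAP*

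**What the plan says.** Section 9.2 defines EFS for every patient entered, "measured from the date of entry to the date of treatment failure, disease relapse, or death from any cause". The censoring rule is that "patients not known to have any of these events are censored on the date they were last examined".

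Section 9.1 gives three treatment-failure categories, two of which are deaths. The third, resistant disease, reads "Failure to achieve CR or CRi or failure to achieve CR, CRi, or PR; only includes patients surviving" at least 7 days "following completion of initial treatment, with evidence of persistent leukemia by blood and/or bone marrow examination". For patients who have not finished treatment, the table provides only for death: "Deaths occurring before completion of therapy".

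Section 6.3 lists reasons to end protocol therapy. Among them is "DLT as defined above or if there is grade 3 neutropenia or thrombocytopenia after holding Venetoclax for four weeks", separate from the item on a marrow showing less than a partial response. Other items are unacceptable toxicity, the physician's judgment and the patient's request. Table 6 takes a patient off study after a gemtuzumab interruption of 7 days or more, and 5.6 allows removal for transplant at any time.

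Under 7.2, patients who stop without progression are followed every 2 months for 6 months, possibly by phone. Section 12.5 limits the efficacy analysis to treated patients whose disease was re-evaluated or who died first. Section 12.6.2 estimates EFS by Kaplan-Meier.

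**The concern.** A patient who leaves during induction, alive and not in remission, has had no success on the regimen. EFS ought to register that, but the definitions supply no event. The patient leaves the risk set, for reasons probably tied to prognosis, or accrues event-free time while on another treatment. With 15 to 24 patients planned (Synopsis; 12.3 says 18 to 24), a few such codings can move the curve visibly, and sites may code the same history differently. Estimating EFS is a stated secondary objective (2.1.2).

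**Working it through.** **1. The definitions applied to one patient.** Take a patient who stops permanently in cycle 1, alive, with no documented response.

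| Possible EFS event | Does it apply? |
|---|---|
| Relapse | No; there was no remission |
| Death in aplasia, or from indeterminate cause | No; the patient is alive |
| Resistant disease, no later blood or marrow evidence | No, on any reading |
| Resistant disease, later evidence present | Not if completion is read literally; yes if stopping counts as completion |
| Progression | Followed for under 7.2, but not an EFS event in 9.2 |

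Where nothing applies, three outcomes remain: censoring at last examination (9.2), an event only at death (9.2), or exclusion if never re-evaluated (12.5). Exclusion conflicts with the 9.2 population.

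**2. Size.** The plan states no EFS estimate, so there is no figure to reproduce. The following is illustrative. Only N comes from the documents (the upper end of the planned range); every other input is assumed.

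- N = 24. A share s stops, uniformly over days 7 to 27.
- Response r = 0.4 among the rest. Responders are dated at day 28, with a median of 6 months (182.6 days) from response to relapse; non-responders fail at day 28.
- Stoppers' median survival from the stop is 4 months (121.8 days).

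Formulas, for t = 61 and 182 days:

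- g(t) = 0.5^((t − 28)/182.6), the share of responders still event-free: 0.882 and 0.557.
- h(t) = the average of 0.5^((t − u)/121.8) over stop days u = 7 to 27, the share of stoppers alive: 0.779 and 0.391.
- Stop scored as failure: F = (1 − s)·r·g.
- Stop censored or excluded: C = r·g.
- Event only at death: D = F + s·h.
- SE = √(F(1 − F)/24).

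Worked case, s = 0.20 at 2 months: F = 0.8 × 0.4 × 0.882 = 0.282. C = 0.4 × 0.882 = 0.353. D = 0.282 + 0.2 × 0.779 = 0.438. SE = √(0.282 × 0.718/24) = 0.092. The shifts are (0.353 − 0.282)/0.092 = 0.77 SE and (0.438 − 0.282)/0.092 = 1.70 SE.

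| s | Month | F | C | D | SE | Shift, C to D (SE units) |
|---|---|---|---|---|---|---|
| 5% | 2 | 0.335 | 0.353 | 0.374 | 0.096 | 0.18 to 0.40 |
| 5% | 6 | 0.212 | 0.223 | 0.231 | 0.083 | 0.13 to 0.23 |
| 10% | 2 | 0.318 | 0.353 | 0.396 | 0.095 | 0.37 to 0.82 |
| 10% | 6 | 0.201 | 0.223 | 0.240 | 0.082 | 0.27 to 0.48 |
| 20% | 2 | 0.282 | 0.353 | 0.438 | 0.092 | 0.77 to 1.70 |
| 20% | 6 | 0.178 | 0.223 | 0.257 | 0.078 | 0.57 to 1.00 |

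Kaplan-Meier simulation under these assumptions agrees. With N = 15 the SE multiples shrink by √(15/24) = 0.79; the differences in EFS do not change.

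**3. The benign reading.** If stopping counts as completion and persistent leukemia is recorded at the nominal 30-day visit, stops on days 7 to 27 become events on days 37 to 57. Both precede day 61, so the estimate equals F at both times and the shift is zero. The ±7-day window in 7.1 could push the latest visits to day 64, just past the 2-month mark.

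**4. Cross-check by patient count.** Let k of 18 patients stop at 0.5 month, the others' median EFS be m = 3 or 6 months, and stoppers' median survival be d = 3 or 6 months. At 6 months, failure scoring gives (1 − k/18)·0.5^(6/m) and censoring or exclusion gives 0.5^(6/m). Event at death adds (k/18)·0.5^(5.5/d) to the failure figure. With k = 1 and m = 3: 0.236 against 0.250 to 0.266. With k = 4 and m = 3: 0.194 against 0.250 to 0.312. Over all settings the overstatement is about 1.4 to 3 percentage points for one patient and 6 to 12 for four.

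**The case against.** Three stronger readings are tempting, and the documents support none of them.

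*About a fifth of patients take this path.* Section 12.3 says the design "selects a dose with toxicity rate near 0.2". That is a DLT rate at the selected dose, not a rate of early stopping without response across the trial. With 6 escalation and 6 expansion patients at that dose it implies 12 × 0.2 = 2.4 DLTs of any kind. A hematologic DLT under 5.2 needs a leukemia-free marrow and cytopenia persisting to day 56, so it does not lead here. A non-hematologic DLT, "any grade 3 or worse treatment-related toxicity occurring within the first cycle", may fall late in the cycle or in a responder (6.1.2 gives 56 days instead; the two must be reconciled, but this point does not turn on it). Tables 5 and 8 describe interruption and resumption for hepatic elevations and tumor lysis, so 6.3 cannot be taken to end therapy in every such case.

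*Every early stopper is missed.* Resistant disease accepts blood evidence. The calendar has a blood count with differential at the safety visit and in long-term follow-up, and 5.4 does not cancel the day-28 marrow for stoppers. Many non-responders would be documented. What survives is that follow-up may be by phone, that some patients will have no later evidence, and that 9.1 never says when initial treatment is complete, so coding depends on the reader.

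*Any stop before a documented response should be a failure.* That would score as a failure a patient who stops on day 10 and is in remission on the day-28 marrow, while RFS counts the same patient as a remission. It would also score patients removed early for transplant as failures. Whether to do so is a choice of estimand, so the fix has to be narrower.

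It is also fair to say that the stakes are modest. No hypothesis, threshold or dose decision depends on EFS, and the effect of censoring alone at a 20% stop rate is below one SE.

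**Conclusion.** The gap is real and its direction is clear. A cycle-1 stopper who is alive, without a documented response and without later evidence of leukemia has no EFS event under 9.1 and 9.2; on a literal reading of completion, nor does one with such evidence. Censoring, waiting for death and exclusion under 12.5 each overstate EFS compared with scoring a failure.

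The size is not determined by the documents, which give no rate for this group. On the assumptions above it is about 0.1 to 0.4 SE at a 5% stop rate, 0.3 to 0.8 at 10% and 0.6 to 1.7 at 20%, and about zero if stoppers are coded resistant disease by the 30-day visit. The top of the range requires that no stopper is documented with leukemia before death. A secondary, descriptive endpoint is affected; the MTD and recommended dose are not. It is worth correcting before analysis because the remedy is small.

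**What to change.** - **9.2, EFS row.** Add that a patient who permanently stops protocol therapy, or starts other anti-leukemic therapy, before any CR, CRi or PR counts as a treatment failure, provided that none of these responses is documented at the end-of-induction assessment or before other anti-leukemic therapy begins. Date the event at discontinuation, or at the new therapy if earlier.
- **9.1.** State that permanent discontinuation ends initial treatment, so that later blood or marrow evidence can be classified.
- **12.5.** State that EFS uses the 9.2 population, without the re-evaluation requirement.
- **12.6.2.** Add a sensitivity analysis that censors patients removed for transplant before response assessment.

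The cost is a few sentences. The reason for discontinuation (6.3) and subsequent therapy (study calendar) are already recorded, and no treatment rule changes. The downside is a somewhat lower reported EFS.
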